9.1.3. Co-Primary Efficacy Sensitivity Analyses

A number of sensitivity analyses will be performed to assess the robustness of the results of the primary analyses and to test the assumptions of the MMRM model. Details of statistical methods for these sensitivity analyses are described below:

- The primary efficacy analyses will be repeated using the mITT and PP populations.
- Separate models including a treatment-by-study center effect will be utilized to assess if treatment effects differ by study center. If the treatment-by-study center interaction term is significant in either model the co-primary efficacy results will be summarized descriptively by study center (possibly pooled).
- Using the primary efficacy MMRMs, the average of Days 42 and 84 will be compared between treatments using linear contrasts for both co-primary efficacy endpoints.
- To determine if the primary efficacy results are affected by subjects who withdraw early from the trial, the TNmAS-MAL and CGIC scores for subjects who withdraw from the trial early will be compared graphically with the scores for subjects who completed the trial. The last observed TNmAS-MAL and CGIC score captured prior to early termination will be plotted and compared against the average TNmAS-MAL and CGIC scores calculated from subjects who complete the trial. This type of plot will illustrate if subjects who dropout early from the study are performing better or worse than those subjects who complete the study.
- To ensure that subjects who withdraw early from the trial with “good” TNmAS-MAL and CGIC scores do not unduly bias the results of the primary efficacy analyses in a positive direction, subjects who withdraw early from the trial will be penalized. In this analysis, subjects will be penalized for withdrawing early from the trial with a “good” TNmAS-MAL or CGIC score. Subjects who withdraw early from the trial will be penalized more.

The procedure used to penalize these subjects for TNmAS-MAL follows. First, determine the median TNmAS-MAL change from baseline score using only scores less than 0 (indicating improvement) within treatment group at each visit. Note that subjects whose scores are greater than or equal to 0 are not used when calculating the

[figure not shown]
median. For any subject that discontinues for any reason, check to see if his or her TNmAS-MAL change from baseline score for the current visit is less than the median for the current visit described above (do this for every visit for which the subject has a score available). If the early termination visit falls between two scheduled visits, the medians calculated from the scheduled visits will be interpolated to the termination time. If the subject's score is less than the median at that visit, then scale the subject's current score by multiplying it by the subject's last week that the TNmAS-MAL score is observed divided by 12. For example, if a subject discontinues and has the final TNmAS-MAL score at Week 7, then anytime the subject has a score less than the respective within treatment/visit median described above, that score will be multiplied by 7/12. These new scores are then used in the primary efficacy MMRM model.

A similar approach will be used for CGIC. CGIC values of 1 (very much improved), 2 (much improved), or 3 (improved) will be utilized to determine the median.

- The impact of missing data will be determined in an analysis using an analysis of covariance (ANCOVA) model based on multiple worst observation carried forward (mWOCF) imputed data. For mWOCF imputed data, subjects who withdraw from the trial early due to an AE will have their missing data imputed using WOCF; all other missing data will be imputed using the last observation carried forward (LOCF). The models will include treatment and study site as fixed effects. The model for TNmAS will also include baseline score as a covariate.
- The primary efficacy analysis model (MMRM) makes the assumption that missing data are “missing at random” (MAR). When data are MAR, the missingness of the data does not depend on the missing value after conditioning on the observed data (i.e., prior assessments and baseline covariates). Note that when the missingness of the data depends on the values of the missing variables after conditioning on the observed data, the data are called “missing not at random” (MNAR). In order to assess the MAR assumption, a placebo-based pattern mixture model (PMM) will be utilized following the steps outlined in Ratitch B and O’Kelly, M.J. (2011) for both TNmAS-MAL and CGIC.

[figure not shown]
Briefly, the strategy for implementing this approach is as follows for subjects with missing data:

1. Impute all non-monotone (intermittent) missing data using the MCMC method of PROC MI. Note that this imputation will sample data within each treatment group. SAS pseudo code is provided below.

2. Using the imputed datasets from Step #1 that are now monotone missing (no intermittent missing data), a single call to PROC MI (including the MNAR statement) will be utilized to impute the monotone missing data. Additional details are provided below.
 - Within the call to PROC MI, one timepoint is imputed at a time. Day 42 first, then Day 84.
 - When imputing at time-point t , the imputation step will include all placebo subjects, but only those from the active arms that have a value missing at time-point t . Subjects with non-missing data that are on active arms will not contribute to the estimation for this step.
 - Repeat the above step for all timepoints t . Thus, the data for timepoint $t+1$ (Day 84) uses the data imputed from previous timepoints (Day 42).

SAS pseudo code is provided below. SAS accomplishes this iterative process in one step. Note that the treatment level 3 is the placebo treatment group:

3. When all missing data are imputed, the MMRM models, as described in Section 9.1.2, will be used to analyze the TNmAS-MAL and CGIC endpoints. PROC MIANALYZE will be used to combine the parameters from the analyses for inference.
 - The above PMM and MMRM analyses will be repeated using only two arms (Placebo and AERT 40 mg). The overall treatment effect could be diluted by the AERT 80 mg dose if there a significant number of discontinuations at this dose level compared to the AERT 40 mg dose, and these analyses serve to compare to Placebo without that possibility. Additionally, this analysis will be completed on Placebo and AERT 80 mg arms, in the unlikely event that there is a trend in the lower dose level causing discontinuations.

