12.4 Withdrawal of Subjects

Withdrawn subjects are those who do not complete all evaluations and procedures outlined in the protocol. A subject will be considered to have discontinued prematurely if he/she withdraws after being randomized and prior to completing Visit 6 (Final Visit). Subjects who discontinue taking study drug for any reason for greater than 5 consecutive days must also be withdrawn from the study. Subjects may be withdrawn from the study because of any of the following:

- **Adverse Event:** An AE that, in the opinion of the Investigator or Sponsor, suggests that continued participation in the study is not in the subject's best interest for safety reasons (also see [Section 10](#)). All AEs that are present when the subject withdraws from the study will be followed as described in [Section 9.7.4](#).
- **Medical Condition:** Any medical condition that, in the Investigator's judgment, would increase the risk or interfere with the evaluation of study objectives.
- **Lost to Follow-up:** As per the comprehensive lost to follow-up guidance document that will be submitted to the IRB/IEC with the clinical protocol.
- **Subject Request:** Subject requests for any reason to be withdrawn or withdraws his/her consent.
- **Protocol Deviation:** A subject may be withdrawn from the study at the discretion of the Investigator or Sponsor due to poor compliance with protocol requirements that may compromise the study results or subject safety.
- **Enrollment in Another Study:** Enrollment in other protocols involving research drugs, medical devices, or surgeries.
- **Other Anti-spasticity Treatment:** Starting any other pharmacological anti-spasticity treatment during the study.

- **Relapse:** Subjects who experience an acute MS exacerbation/relapse (symptoms including but not limited to visual disturbance, dizziness, tingling, or extreme fatigue lasting greater than 24 hours and occurring at least 30 days after a previous relapse) requiring immediate therapy or adjustment in disease-modifying medication dose (eg, oral or intravenous high-dose steroid therapy). Upon resolution of symptoms, the subject may choose to be assessed for entry into the subsequent open-label extension study (Study OS440-3005).

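### The TNmAS-MAL early-withdrawal penalty has no cap at 1 and uses each arm's own median, so it can enlarge some taper-period withdrawals' improvements and can be laxer on AERT than on placebo

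*SAP*

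**What the plan says.** SAP 9.1.3 gives the aim of this analysis: withdrawals with good scores should "do not unduly bias the results of the primary efficacy analyses in a positive direction". It also gives the intended gradient: "Subjects who withdraw early from the trial will be penalized more". Protocol 11.4.1 states the same idea and ties the size of the penalty to time in the trial, but gives no formula.

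For TNmAS-MAL the SAP procedure has three parts.

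- **Threshold.** "determine the median TNmAS-MAL change from baseline score using only scores less than 0 (indicating improvement) within treatment group at each visit". The worked example repeats that the rule applies "anytime the subject has a score less than the respective within treatment/visit median described above".
- **Penalty.** The score is scaled by "multiplying it by the subject's last week that the TNmAS-MAL score is observed divided by 12". In the example the last score is at Week 7, and "that score will be multiplied by 7/12". No maximum is given, and week is not defined as actual days over 7, a rounded number or the nominal visit week.
- **Who is covered.** Every discontinued subject, whatever the reason, at each visit where that subject has a score.

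Protocol 12.4 says: "Withdrawn subjects are those who do not complete all evaluations and procedures outlined in the protocol". Its next sentence treats a randomised subject as prematurely discontinued if withdrawal comes at any point before Visit 6 is completed. That includes the taper period, after the Day 84 assessment. Protocol 6.5 requires a TNmAS-MAL assessment at the early termination visit.

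**The concern.** A stress test of this kind should only pull results toward no improvement, and it should judge a given score the same way in every arm. As written, the rule can fail on both counts.

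First, a subject who leaves during taper may have complete Day 42 and Day 84 data. Nothing is missing at the primary time point, yet the subject falls under the rule. A last score after Week 12 then gives a multiplier above 1, and the intended reduction becomes an increase.

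Second, an own-arm threshold moves with that arm's response. If AERT improvers do better, the bar for calling an AERT withdrawal's score good rises, so the test loosens in the arms it is meant to challenge. SAP 9.1.3 itself foresees heavier discontinuation at 80 mg, so unequal withdrawal is a realistic setting.

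What is at stake is the credibility of one robustness analysis of a co-primary endpoint, not the primary test.

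**Working it through.** **Inputs from the documents.** Factor = last week / 12, and the own-arm median of improvers at each visit (SAP 9.1.3). Visit 5 is Day 84 ± 5, so Days 79 to 89 (Protocol Table 1). TNmAS-MAL is the sum of three joint scores of 0 to 5, so an integer from 0 to 15 (Protocol 8.1 and Appendix 1). There are 170 subjects per arm (Protocol 5; 3 × 170 = 510). The documents as available show no effect size, SD or withdrawal rate, so those are assumed below.

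**1. The plan's own figure.** Week 7 gives 7/12 = 0.583, as in the SAP example.

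**2. The factor by day of last score**, with f = (day/7)/12:

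| Last score | f, actual days | f, week rounded up | f, week rounded down | A change of -3 becomes (actual days) |
|---|---|---|---|---|
| Day 42 | 0.500 | 0.500 | 0.500 | -1.50 |
| Day 77 | 0.917 | 0.917 | 0.917 | -2.75 |
| Day 84 | 1.000 | 1.000 | 1.000 | -3.00 |
| Day 85 | 1.012 | 1.083 | 1.000 | -3.04 |
| Day 89 | 1.060 | 1.083 | 1.000 | -3.18 |
| Day 91 | 1.083 | 1.083 | 1.083 | -3.25 |

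With the nominal Week 12 for Visit 5, a subject last scored at that visit has f = 1. At f = 1.083 and a change of -3, each 1% of an arm affected moves that arm's simple mean by 0.01 × (3.25 - 3.00) = 0.0025 points.

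**3. The threshold.** A score is penalised only if it is strictly below the own-arm median.

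- Assumed medians of -2 (placebo) and -4 (AERT), Week 7, change -3: placebo becomes -3 × 7/12 = -1.75; AERT stays -3.
- Assumed medians of -2 and -3, Week 6, change -3: placebo becomes -3 × 6/12 = -1.5; AERT stays -3.
- The medians need not differ. For normally distributed changes rounded to integers, means of -1 and -2 give improver medians of -2 and -3 at SD 2.5, but -3 in both arms at SD 3. If placebo has the more negative median, the asymmetry runs the other way.

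**4. Effect on the Day 84 difference (AERT minus placebo).** This was simulated with a two-visit maximum-likelihood model without centre or baseline terms, 170 per arm, integer scores and 600 replicates per scenario. Assumed: SD 2.5, between-visit correlation 0.6, withdrawal on Days 26 to 91, factor uncapped. Selected scenarios:

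| Mean change, placebo / AERT | Withdrawal, placebo / AERT | No penalty | Own-arm (SAP) | Pooled median | Placebo median |
|---|---|---|---|---|---|
| -1 / -2 | 10% / 25% | -1.003 | -0.943 | -0.934 | -0.924 |
| -1 / -2 | 20% / 35% | -1.024 | -0.950 | -0.936 | -0.922 |
| -1.5 / -2.5 | 10% / 10% | -1.006 | -0.990 | -0.987 | -0.986 |
| -1.5 / -2.5 | 20% / 35% | -0.998 | -0.902 | -0.893 | -0.886 |
| -1.5 / -3 | 20% / 35% | -1.497 | -1.383 | -1.351 | -1.344 |

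The largest gap is in the last row: 1.383 - 1.344 = 0.039. The smallest is in the third: 0.990 - 0.987 = 0.003. Where AERT was better, 11% to 25% of the AERT withdrawals that the placebo threshold would penalise were spared. With equal true means that share was about 8%, which is chance.

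**5. A larger assumed effect.** A single-visit simulation used means of -1 and -3, SD 2.5, withdrawal of 15% and 25%, and withdrawal in Weeks 3 to 11. The difference went from -2.00 without a penalty to -1.86 (own-arm), -1.81 (pooled) and -1.79 (placebo median). The gaps are 0.05 and 0.07. The amounts removed are 0.14, 0.19 and 0.21, so the own-arm rule removes about a quarter to a third less than a common threshold.

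None of these runs isolates the effect of the missing cap. Its size rests on steps 2 and 3 alone.

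**The case against.** The own-arm median is stated twice, so it looks deliberate: good may be meant as good for that arm. A common threshold is not even-handed in outcome either. In the 2-point simulation the pooled median penalises 16% of placebo and 42% of AERT withdrawals, against 24% and 35% under the SAP rule. The absolute gaps are hundredths of a point on a 0 to 15 scale. The SAP also has an mWOCF ANCOVA, a placebo-based pattern-mixture model and a dropout plot that address the same worry. All of this stands, and it limits the importance of the point.

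A reader might infer more than the documents support, in two ways.

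- **That the rule turns the analysis in AERT's favour or gives false reassurance.** It does not. In every simulated scenario with a benefit, the penalised difference was smaller than the unpenalised one, and under the SAP rule a larger share of AERT than of placebo withdrawals was penalised in the 2-point run. The shortfall exists only relative to a common threshold, and only if the medians fall in that order.
- **That late withdrawals in general are rewarded.** They are not. A last score at Week 11 is still shrunk (0.917). A factor above 1 needs a last score after Day 84 and, before Day 91, a week taken from actual days or rounded up. Factors for Day 92 (1.10) or Day 97 (1.15) would need a subject scored at Visit 6 who still counts as not having completed it, which is an edge case.

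The objection does not remove the fact that a rule described as a penalty can enlarge an improvement, or that its threshold depends on the treatment effect under test.

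**Conclusion.** The point holds as a defect in the specification of one sensitivity analysis.

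- **Cap.** Protocol 12.4 and the uncapped factor together allow multipliers of 1.01 to 1.08 for last scores on about Days 85 to 91, applied to better-than-median improvements of subjects who may have full Day 42 and Day 84 data. This depends on how week is read.
- **Threshold.** If the AERT improver median is more negative than placebo's, the rule is laxer on AERT for scores between the two. Compared with a common threshold, that is worth about 0.00 to 0.04 points on the Day 84 difference for effects of 1 to 1.5 points, and up to about 0.07 for an assumed 2-point effect. It vanishes if the medians tie and reverses if they order the other way.

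These sizes rest on assumed means, SDs and withdrawal rates and on models simpler than the planned MMRM. The primary analysis and its 0.05 level are not affected.

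**What to change.** In SAP 9.1.3, before unblinding:

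1. Apply the penalty only to subjects who withdraw without a Visit 5 (Day 84) assessment. State whether an early-termination score mapped to Visit 5 under SAP 7.3.3 counts as one.
2. Define week (for example, actual study day of the last score divided by 7) and use min(1, week/12). The Day 85 to 91 factors then fall from 1.012–1.083 to 1.000.
3. Use one threshold for all arms at each visit, either the placebo or the pooled median of improvers, chosen now. Interpolate between visits from the same common medians.
4. Carry the cap and the common threshold into the CGIC version. The CGIC codes used there must separately be reconciled with the -3 to +3 scale in Protocol Appendix 3.

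The cost is a few lines of SAP text and programming. Protocol 11.4.1 gives only the concept, so its visible text need not change. The downside for the sponsor is that this sensitivity result may become slightly less favourable to AERT.

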8.2 Clinical Global Impression of Change

The CGIC was developed for use in National Institute of Mental Health (NIMH)-sponsored clinical trials to provide a brief, stand-alone assessment of the clinician's view of the subject's global functioning prior to and after initiating a study medication (Guy 1976). The CGIC scale will be used to measure the overall change in the subject's condition since starting the study.

In clinical research, the CGIC is administered by an experienced clinician who is familiar with the disease under study and the likely progression of treatment. Consequently, the CGIC rater can make an expert clinical global judgment about the severity of the illness across various time points within the context of that clinical experience. The clinician makes a judgment about the total picture of the subject at each visit: the illness severity, the subject's level of distress and other aspects of impairment, and the impact of the illness on functioning. The CGIC is rated without regard to the clinician's belief that any clinical changes are or are not due to medication and without consideration of the etiology of the symptoms.

The investigator will evaluate the subject's status on a -3 to +3 scale judging whether there had been a change from significant worsening to significant improvement relative to Visit 2 (Baseline) and must have access to the TNmAS. The CGIC scale is provided in Appendix 3.

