8.3 Patient Global Impression of Change

The PGIC is a standard instrument that is a well validated outcome measure. The 7-point PGIC measures change in the subject's overall status using the following categorical scale:

- 1 = Very much improved
- 2 = Much improved
- 3 = Improved
- 4 = No change
- 5 = Minimally worse

- 6 = Much worse
- 7 = Very much worse

The PGIC will be done at the visits specified in Table 1. The PGIC is provided in Appendix 4.

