Appendix 3. Clinical Global Impression of Change Scale

Based on your assessment of the subject since Visit 2 (Baseline), please rate the change in overall global functional performance of the subject as she/he appears today. Your opinion should not be limited to the level of spasticity the subject is experiencing.

In other words, compared to her/his condition at Baseline, how much has she/he changed?

-3	Significantly worse compared to visit 2
-2	Moderately worse compared to visit 2
-1	Slightly worse compared to visit 2
0	No change
+1	Slightly improved compared to visit 2
+2	Moderately improved compared to visit 2
+3	Significantly improved compared to visit 2

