5. STUDY METHODS

5.1. General Study Design and Plan

As background for the statistical methods presented below, this section provides an overview of the study design and plan of study execution. The protocol is the definitive reference for all matters discussed in what follows.

This is a multicenter, randomized, double-blind, placebo-controlled, parallel-group study to evaluate the safety and efficacy of oral AERT in MS patients with spasticity. Two doses of AERT, 40 mg and 80 mg, will be compared with placebo. The treatment groups will be randomized in a 1:1:1 ratio. There will be a 9-day titration period, then a 75-day maintenance period, followed by a 7-day taper period.

Eligible subjects will undergo an at least 14-day washout period for withdrawal of all medications used for anti-spasticity and/or muscle relaxation prior to randomization. A baseline clinical evaluation will be performed (Visit 2) to confirm eligibility for study randomization, and subjects will be assigned to 1 of 3 treatment arms: (1) AERT 40 mg; 2) AERT 80 mg; or 3) placebo. During the first 9 days of drug administration, doses will be titrated about every 3 days to a fixed-dose of either AERT 40 mg, AERT 80 mg, or placebo BID. Subjects will remain at that fixed-dose for 75 days. At the end of the maintenance period, the subject's dose will be tapered for an additional 7 days before the subject returns to the site for a final safety evaluation at Day 92 (Visit 6).

The study design schema is presented in Figure 1. The schedule for assessments is presented in Table 1.

Figure 1 Study Design Schema

[figure not shown]

Table 1 Schedule of Assessments

Procedure	Screening Visit 1 Days -21 to 0	Baseline Visit 2 Day 1 (±3 days)	Visit 3 Day 10 (±3 days)	Visit 4 Day 42 (±5 days)	Visit 5 Day 84 (±5 days)	Final or Early Termination Visit 6 Day 92 (±5 days)
Written informed consent	X					
Inclusion and exclusion criteria	X	X				
Review study discontinuation criteria		X	X	X	X	
Withdrawal anti-spasticity medication	X					
Assign enrollment number	X					
Randomization		X				
Demography	X					
Medical/surgical history	X					
Physical examination	X					
Height	X					
Weight	X					X
Vital signs1	X	X	X	X	X	X
Hematology/serum chemistry/urinalysis	X	X	X	X	X	X
Electrocardiogram	X					X
Pregnancy test2	X	X	X	X	X	X
Dispense study medication		X	X	X	X	
Collect unused study medication			X	X	X	X
C-SSRS	X	X	X	X	X	X
TNmAS-MAL3	X	X		X	X	X
EDSS	X	X				X
CGIC				X	X	X
PGIC						X

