5.3. Analysis Variables

Variables to be analyzed include demographics and baseline characteristics, safety variables (adverse events, clinical laboratory investigations, vital signs, ECGs, USP questionnaire, and C-SSRS), and efficacy variables (TNmAS-MAL, CGIC, PGIC, EDSS, and TNmAS-TL). See Section 8 of the protocol for further details on the efficacy variables. Derived variables from study endpoints are described with the sections describing the analyses for these endpoints.

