7.3.3. Handling of Early Termination Visit Information

If a subject is terminated early from this study the early termination visit data will be analyzed at the closest scheduled visit. If the closest visit has valid data, the early termination data will be assigned to the next available visit.

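### SAP 9.1.3 labels the improved CGIC values in the wrong direction and states no CGIC penalty trigger, so this sensitivity analysis can be coded against its own purpose

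*SAP*

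**What the plan says.** Protocol 8.2 has the investigator rate CGIC "on a -3 to +3 scale judging whether there had been a change from significant worsening to significant improvement". In Protocol Appendix 3, +1 is slight improvement, +2 moderate, and +3 is "Significantly improved compared to visit 2". Higher is better and 0 is no change.

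The SAP does not redefine the scale. Section 5.1 states: "The protocol is the definitive reference for all matters discussed in what follows". Section 5.3 adds: "See Section 8 of the protocol for further details on the efficacy variables".

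SAP 9.1.3 includes a penalised analysis, so that early withdrawals with good scores "do not unduly bias the results of the primary efficacy analyses in a positive direction". For TNmAS-MAL the procedure is complete. Within treatment and visit, take the median of the negative (improved) changes. If a withdrawn subject's change is below that median, multiply it by the last observed week divided by 12.

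For CGIC there are two sentences. One says a similar approach will be used. The other is: "CGIC values of 1 (very much improved), 2 (much improved), or 3 (improved) will be utilized to determine the median".

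The PGIC list in Protocol 8.3 begins "1 = Very much improved", and its labels for 2 and 3 also match those the SAP gives to CGIC. The PGIC form in Protocol Appendix 4 differs from both: there 1 is no change or worse, and 7 is best.

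**The concern.** The SAP's labels make 1 the best CGIC value, whereas the protocol makes +1 the weakest improvement. The label slip alone would be harmless. It matters because the SAP states no comparison for CGIC, and the only one written down is for an outcome where lower is better. A programmer who follows the labels and the written trigger would keep the below-median comparison. One who follows the stated purpose would reverse it. The two programs would penalise different subjects in a pre-specified check on a co-primary endpoint. If the question is settled after unblinding, the direction is chosen with the results in view.

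**Working it through.** **Inputs.** CGIC values -3 to +3 (Protocol 8.2, Appendix 3); improver set {1, 2, 3}, factor w/12 and the below-median trigger (SAP 9.1.3). Here s is the score, m the improver median and w the last observed week.

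**1. The SAP's own example.** A last score at Week 7 gives 7/12 = 0.583. For TNmAS-MAL with an illustrative m = -3, a change of -6 is below m and becomes -6 × 7/12 = -3.5, a smaller improvement. The rule works as intended there.

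**2. Is the CGIC median wrong?** No. Improvement on the protocol's scale is +1, +2 or +3, so {1, 2, 3} is the correct set whatever the labels say. Its median lies between 1 and 3. Non-integer medians can arise from even counts or from the interpolation to the termination time.

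**3. The written trigger carried over (scale if s < m), w = 7:**

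| Score | Scaled when | Result |
|---|---|---|
| -3 | always | -1.75 |
| -2 | always | -1.17 |
| -1 | always | -0.58 |
| 0 | always | 0 |
| +1 | m above 1 | 0.58 |
| +2 | m above 2 | 1.17 |
| +3 | never | +3 |

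The best withdrawals escape the penalty and the worst ones improve.

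**4. The mirrored strict trigger (scale if s > m), w = 7.** +3 becomes 1.75 at any m below 3, and +2 becomes 1.17 at any m below 2. +1, 0 and all negatives are unchanged. At m = 3 nobody is penalised.

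**5. The mirrored trigger including ties (scale if s ≥ m), w = 7.** +3 becomes 1.75 at every m, +2 becomes 1.17 at m up to 2, and +1 becomes 0.58 at m = 1.

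**6. Coding CGIC as the labels imply (1 best).** At m = 2, the below-median rule takes 1 to 0.58, which is a better value and so again not a penalty.

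**7. The factor is not always below 1.** Protocol 12.4 counts a subject who leaves after Visit 5 but before completing Visit 6 as a premature discontinuation, and Visit 5 is Day 84 ±5. At Day 84 the factor is 12/12 = 1. At Day 89 it is (89/7)/12 = 1.06, so a scaled +3 would become 3.18, off the scale. Steps 3 to 5 therefore describe a last observed week before 12.

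**8. Effect on the treatment difference.** The documents give no CGIC means or SD, so these inputs are assumptions: rounded and clipped normal scores, SD 1.2, 15% of placebo and 25% of AERT subjects withdrawn at Week 6 (factor 6/12). Differences in simple means, AERT minus placebo:

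| Placebo/AERT means | Unpenalised | Carried over | Strict mirrored | At or above |
|---|---|---|---|---|
| 0.3/0.8 | 0.491 | 0.487 | 0.437 | 0.418 |
| 0.5/1.0 | 0.487 | 0.444 | 0.481 | 0.446 |
| 0.3/0.8, withdrawn averaging -0.5 in both arms | 0.287 | 0.325 | 0.282 | 0.275 |

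Strict mirrored minus carried over: 0.437 - 0.487 = -0.050; 0.481 - 0.444 = +0.037; 0.282 - 0.325 = -0.043.

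Over 14 input sets (these two mean pairs, several withdrawal patterns), the shift from the unpenalised difference runs from -0.045 to +0.055 carried over, -0.054 to +0.014 strict mirrored, and -0.073 to -0.002 at or above.

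An approximate Day 84 contrast, with withdrawn subjects contributing Day 42 only, gives -0.029 to +0.037, -0.035 to -0.001 and -0.048 to -0.002. Its limit is that under SAP 7.3.3 "early termination visit data will be analyzed at the closest scheduled visit", so some later termination scores would enter at Day 84.

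**The case against.** The strongest reply is that the SAP already answers the question. Its purpose is to penalise good scores, it explains the sign convention for TNmAS-MAL, and it calls the CGIC method similar, not identical. A careful programmer would mirror the comparison. Much of this stands: the purpose does imply a mirrored trigger, and the literal rule contradicts it. What remains is that the one sentence specific to CGIC carries labels under which lower is better, and the SAP does not resolve the conflict.

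On ties, the written TNmAS-MAL trigger is strict, so carrying it over in mirrored form would leave a score equal to the median unscaled. That is a fair default. Scaling ties as well is a preference that departs from the written rule: with a median of 1 it also penalises +1, a slight improvement. Nor would it always penalise +3, because the factor reaches 1 at Day 84.

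A reader might infer that the median is computed from the wrong values, or that the plan commits the sponsor to a reversed penalty. The documents support neither. The numerals are right on the protocol's scale, and no CGIC trigger is written at all.

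**Conclusion.** The labels are an error, shown by setting SAP 9.1.3 beside Protocol 8.2 and Appendix 3. The trigger direction is left to inference. The score-level results are exact for a last observed week before 12. The effect on the treatment difference is small, can go either way, and rests wholly on assumed means, SD and withdrawal rates.

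A reader might infer that the co-primary CGIC result is at risk. It is not. The primary MMRM, the alpha level, the success rule, the mWOCF ANCOVA and the placebo-based pattern-mixture model do not use this penalty. Severity is minor.

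**What to change.** Before unblinding, amend SAP 9.1.3 as follows:

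- Replace the CGIC labels with those of Protocol Appendix 3 and define improvers as +1, +2 and +3.
- State that a withdrawn subject's CGIC score is multiplied by the last observed week over 12 when it is greater than the within-treatment, within-visit median of the positive scores, and that scores of 0 or below are unchanged.
- Say how ties are handled. The strict rule parallels TNmAS-MAL, and the SAP should note that it penalises nobody at a median of 3. If the sponsor prefers to scale scores at or above the median, the SAP should say so.
- Cap the factor at 1.

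The cost is a few sentences and a small change in code. The CGIC sensitivity estimate may end up slightly more or less favourable to AERT than under the literal rule. One limit remains: a scaled score can fall below an unscaled lower one (at Week 7 and median 2, +3 becomes 1.75 while +2 stays at 2). The TNmAS-MAL rule has the same property, so this is not a reason against the change.
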